The primary aim of this phase of the project is to execute a pilot feasibility trial to evaluate the preliminary efficacy of, usability of, and satisfaction with the VPMRC.

The primary hypothesis is that a clinically meaningful reduction in pain interference with functioning post-exposure to the VPMRC will be observed compared to baseline ratings.

The secondary hypothesis is that Veterans who participate in the VPMRC will report a clinically meaningful reduction in pain intensity and statistically significant improvements on other important

problems commonly associated with CLBP including fatigue, sleep problems, depressive symptoms and negative mood, relative to baseline.

The tertiary hypothesis is that participants will report high levels of interest (credibility), use, and satisfaction with the VPMRC.

3. Background:

Limitations of current interventions for CLBP

For years, the practice of pain medicine has over-emphasized expensive and modestly effective treatments for CLBP, while under-utilizing inexpensive evidence-based behaviorally-oriented approaches that have demonstrated comparable or superior effect.^{1,2,3,4,5} Non-pharmacological treatments such as education, exercise, and behaviorally-based therapies have been demonstrated to be efficacious and effective, but are rarely used in routine clinical practice. Optimal care should combine both pharmacological and non-pharmacological behavioral interventions – but again, this is rarely done. Patients have historically considered behavioral interventions to be “mental health” resulting in reluctance to accept the need for a “psychological” treatment for their pain. It is imperative that a viable delivery platform be developed to facilitate Veteran access to efficacious non-pharmacological interventions. Such integrated delivery has become the “gold standard” of care for other chronic medical conditions such as diabetes, congestive heart failure, and asthma. The development of the Veterans Pain Management Resource Center (VPMRC) represents a necessary “first step” in providing comparable evidence-based disease management for CLBP – a long anticipated transformation in how clinical pain medicine is practiced.

Behavioral interventions for pain self-management

Cognitive-behavioral therapy

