The primary aim of this phase of the project is to execute a pilot feasibility trial to evaluate the preliminary efficacy of, usability of, and satisfaction with the VPMRC. A single treatment condition (Usual Care [UC] plus VPMRC) X two evaluation periods (baseline and 10 weeks post-baseline) design with multiple dependent measures will be employed. Participants in the study will be 55 Veterans with CLBP. Participants will continue to receive care as usual from their primary care providers (PCPs) and other healthcare providers.

Recruitment

VistA Search: We will identify potential Veterans for inclusion from available electronic medical record (EMR) data in VistA. All Veterans 18 years or older from VACHS (Station 689) with low back pain defined using the *International Classification of Diseases, Ninth Revision* diagnostic codes related to low back pain (724, 7240x, 7241x, 7242x, 7243x, 7244x, 7245x, 7246x, 7247x, 8460x, and 8472x) will be considered eligible. We will attempt to oversample OEF/OIF/OND, female, and minority Veterans, as these Veterans have high prevalence rates of chronic musculoskeletal pain conditions and are of particular interest in the context of the proposed study. We will then identify Veterans in this group to exclude psychiatric hospital admissions in the previous 30 days, suicide flag in the Electronic Medical Record (EMR), or behavioral alert flag in the EMR.

A letter will be sent to the identified Veterans from their PCPs informing them about the study and inviting them to participate. Veterans will be provided with information about the voluntary nature of the study and the option to "opt out" from further contact with study staff by notifying us of their lack of interest by phone, email or letter. Veterans who do not contact us will be called by the study RA to be further informed about the study and, if interested, to be screened for participation. Screening will include several of the key eligibility criteria for the study (e.g., confirmation of presence of CLBP, readiness to engage in self-management for pain, interest in Internet-based pain care, and absence of medical and psychiatric comorbidities). If screening suggests potential eligibility, and if the Veteran is interested, an in-person appointment for obtaining written informed consent and baseline assessment data will be scheduled. Solicitation letters will be mailed in waves in order to prevent overwhelming our capacity to offer participation in a timely manner.

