Because the primary and secondary hypotheses test differences in outcome measure scores across time, we will use paired t-tests, or their non-parametric analogs (e.g., Mann-Whitney test) to compare mean (or median) scores on the outcomes across time. Given the multiplicity of tests for secondary outcomes (i.e., six outcomes) and the power of the study, in addition to maximizing sample size, we will use the Bonferroni procedure p-value, which we conservatively estimate to be $p = 0.008$, based on an overall significance of $p = 0.05/6$, to account for the number of comparisons. Our six secondary outcomes will be examined with the purpose of informing future modifications to the VPMRC and additional hypothesis generation. We have not grouped within subsets in order to ensure a more conservative approach. Tertiary hypotheses will examine data related to usability (use of and functionality) and satisfaction (satisfaction, credibility) with the VPMRC and will be collected only at 10 weeks post-baseline. Descriptive statistics will be employed to examine these data in order to describe participants' experiences with the VPMRC.

As in Phase I, quantitative data from the Post-intervention Measure with added data from the weekly phone calls for Phase II regarding usability of and satisfaction with the VPMRC will be used to modify the program. In addition, we will use specific primary and secondary outcomes data to inform modification of the VPMRC. For instance, if the data suggest a significant reduction in pain interference, but more modest changes in fatigue or depression, specific modules, such as Pacing (the pleasant activity scheduling coping skill) or Adaptive Stress Response (the using positive coping statements coping skill) will be targeted for further content and presentation enhancement to increase benefit to patients on these important related outcomes. We will also use data from tertiary outcomes to further modify presentation of the various treatment modules. For example, if certain modules are clearly preferred, as indicated by participant report of modules completed and satisfaction with the modules, other, less-preferred modules may be further enhanced (e.g., changes to audio-visual aspects, presentation of content within modules) to increase use, interest, and satisfaction.

6. References:

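### Secondary outcomes: Holm's step-down would keep the 5% family-wise guarantee of the planned single-step Bonferroni and never reject fewer hypotheses (optional, low-priority gain)

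*Combined protocol and SAP*

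**What the plan says.** The Phase II part of the Analytic Plan introduces its multiplicity rule with "Given the multiplicity of tests for secondary outcomes (i.e., six outcomes) and the power of the study", and continues that "we will use the Bonferroni procedure p-value, which we conservatively estimate to be" 0.008, derived as 0.05/6. Every secondary outcome therefore faces the same fixed threshold, and no step-down is mentioned. The comparisons over time are within person: "we will use paired t-tests, or their non-parametric analogs". The design has one treatment condition and "two evaluation periods (baseline and 10 weeks post-baseline) design with multiple dependent measures". On sample size, the Design section states: "Participants in the study will be 55 Veterans with CLBP".

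The secondary hypothesis in section 2 (Purpose) predicts a clinically meaningful fall in pain intensity and "statistically significant improvements on other important" problems: fatigue, sleep, depressive symptoms and negative mood. The plan therefore expects several outcomes to improve together. On what the results are for, the Analytic Plan says: "Our six secondary outcomes will be examined with the purpose of informing future modifications to the VPMRC and additional hypothesis generation".

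**The concern.** The plan mentions power when it introduces its multiplicity rule, then adopts the less powerful of two procedures that carry the same guarantee. Bonferroni holds the second, third and later p-values to 0.05/6 even after the smallest one has been rejected. Holm relaxes the threshold after each rejection. The difference matters when several effects are real, which is what the secondary hypothesis predicts. Because part of that hypothesis is worded in terms of statistical significance, the threshold bears on which outcomes are reported as supporting it.

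**Working it through.** **Inputs from the documents.** Six secondary outcomes; overall 0.05; per-test level 0.008; n = 55; paired t-tests.

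**Assumptions, because the documents give no values.** Two-sided tests; standardised mean change d = mean change / SD of change, from 0.2 to 0.6; correlation between outcomes 0 or 0.5; no dropout (n = 55), or 20% dropout (n = 44).

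**1. The plan's own figure.** 0.05/6 = 0.00833, stated as 0.008. The rounding is downward: 6 × 0.008 = 0.048, below 0.05. For independent tests the family-wise error is 1 − (1 − 0.008)^6 = 0.0471. The figure reproduces and the procedure is valid.

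**2. Holm.** Order the p-values from smallest to largest and compare them in turn with 0.05/6, 0.05/5, 0.05/4, 0.05/3, 0.05/2 and 0.05 (0.0083, 0.0100, 0.0125, 0.0167, 0.0250, 0.0500), stopping at the first failure. No threshold is below 0.05/6, so everything Bonferroni rejects, Holm rejects too. If k null hypotheses are true, the first true null to be tested faces a threshold no larger than 0.05/k. The union bound then caps the family-wise error at k × 0.05/k = 0.05, whatever the correlation.

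**3. Simulated error when nothing improves** (n = 55, 20,000 trials). Correlation 0: 4.9% for Bonferroni at 0.008 and 5.1% for Holm. Correlation 0.5: 4.1% and 4.3%. The simulation standard error is √(0.05 × 0.95 / 20,000) = 0.15 points, so 5.1% is consistent with the 5% bound.

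**4. Power for one outcome under the plan.** For a two-sided paired t-test the noncentrality is d√n. At d = 0.4 it is 0.4 × √55 = 2.97 on 54 degrees of freedom. At level 0.008 this gives power of about 59%, in line with the simulations below.

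**5. Average power per truly improved outcome, Bonferroni at 0.008 → Holm, n = 55.**

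| Truth | Correlation 0 | Gain (points) | Correlation 0.5 | Gain (points) |
|---|---|---|---|---|
| One of six, d = 0.4 | 58.9 → 59.5% | 0.6 | 58.7 → 59.2% | 0.5 |
| Three of six, d = 0.4 | 58.1 → 62.3% | 4.2 | 58.9 → 62.7% | 3.8 |
| All six, d = 0.2 | 11.2 → 12.4% | 1.2 | 11.3 → 13.9% | 2.6 |
| All six, d = 0.3 | 30.8 → 36.8% | 6.0 | 31.1 → 39.2% | 8.1 |
| All six, d = 0.4 | 58.7 → 72.3% | 13.6 | 58.3 → 69.9% | 11.6 |
| All six, d = 0.5 | 82.6 → 93.6% | 11.0 | 82.5 → 91.3% | 8.8 |
| All six, d = 0.6 | 95.1 → 99.1% | 4.0 | 95.0 → 98.5% | 3.5 |

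With n = 44, all six at d = 0.4 and correlation 0.5, power goes from 45.8% to 56.6%, a gain of 10.8 points.

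**6. Reading the table.**
- A small part of each gain comes only from undoing the rounding to 0.008. With one real effect that is practically all of it: at correlation 0.5, unrounded Bonferroni also gives 59.2%.
- Holm's first step is Bonferroni at 0.05/6, so the chance of at least one rejection hardly moves. With all six at d = 0.4 and correlation 0.5 it is 91.0% at 0.008, and 91.3% both for 0.05/6 and for Holm.
- Correlation has no consistent effect. Going from 0 to 0.5 raises the gain at d = 0.2 and 0.3 and lowers it from d = 0.4 upward. The number of real effects and their size drive the gain.

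**7. Which tests can be run.** The secondary outcomes listed are pain intensity, mood (POMS), depression (BDI), fatigue (MFI), sleep (MOS) and behavioral goal adherence. Table 4 schedules goal adherence weekly and at 10 weeks but not at baseline, so a baseline-to-follow-up paired test cannot be run on it. Five instruments remain. For five outcomes at d = 0.35 and correlation 0.5, power is 48.1% with Bonferroni at 0.05/5 and 57.8% with Holm.

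**The case against.** The strongest reply is that nothing in the plan is wrong. Bonferroni is prespecified, holds the family-wise error below 5%, and was chosen by authors who say they wanted to be conservative. That stands as far as validity goes. However, the stated wish for conservatism is the reason given for not grouping outcomes into subsets. Holm across all the outcomes also leaves them ungrouped and keeps the same 5% bound.

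A second reply is that a large gain needs most outcomes to improve by a moderate amount. This also stands. The documents give no effect size, SD of change or correlation for these outcomes, and the 12 to 14 points is the top of the range examined.

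A reader might infer four stronger things, none of which the documents support:

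- *That Holm is clearly more powerful at this sample size.* It may be, or the gain may be under 1 point; the missing effect sizes decide.
- *That correlated outcomes are where Bonferroni loses most to Holm.* Holm does not exploit correlation, and the table shows no consistent pattern.
- *That real improvements are thrown away and module revision is misdirected.* In the plan's example, significance is attached to pain interference, the primary outcome, which lies outside the Bonferroni family. Revision is prompted by comparatively modest changes in fatigue or depression, with no 0.008 cut-off. Nothing says that a change with p = 0.02 would be ignored, and the secondary tests are declared hypothesis-generating.
- *That the chance of declaring all six outcomes is what counts.* With all six at d = 0.4 and correlation 0.5 it rises from 20% to 48%, but the plan never requires all six, and one of the six cannot be tested as a paired change.

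A last reply is that neither procedure controls error until the family is defined. That is correct, and the fix covers it: POMS, MFI and MOS Sleep each yield several subscales, and no tested score is named.

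**Conclusion.** The point holds as an efficiency remark of low priority. The planned rule is valid. Holm has the same guarantee and cannot reject fewer hypotheses; both statements are mathematical and need no assumption about the trial. The size of the benefit does rest on assumptions (two-sided tests, equal effects among the outcomes that improve, the stated ranges of d and correlation). At n = 55 it runs from about half a point per improved outcome to about 14 points. The larger values apply if the secondary hypothesis is broadly right and the changes are moderate. The working does not show that the plan will miss real improvements or misdirect the program's revision.

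**What to change.** In the Phase II Analytic Plan, replace the Bonferroni level of 0.008 with: *Holm step-down at overall two-sided 0.05 across the secondary outcomes that have both a baseline and a 10-week score.* Name one score per instrument for pain intensity, POMS, BDI, MFI and MOS Sleep, and leave behavioral goal adherence out of the paired-test family. Report Holm-adjusted p-values, together with the mean change and an ordinary 95% confidence interval for each outcome.

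The multiplicity rule itself takes one sentence, plus a short list of scores that either procedure would need. It requires no extra data or participants. The small downside is that simple simultaneous confidence intervals matching the tests are not available with Holm; the Analytic Plan does not call for any.
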